3.2.2 Exclusion Criteria

Patients with any of the following will be excluded from admission into the study:

- Existence of an intra-abdominal abscess, enteric fistula, or symptomatic bowel obstruction
- History of allergy to salicylates.
- History of short gut syndrome, active ulcer or recent history of GI bleeding or melena.
- Systemic chemotherapy for the treatment of cancer during the 60 days prior to consent or planned during the study

- Presence of ileostomy or colostomy, or history of prior gastric resection or significant colon resection
- Intra-abdominal surgery within the past 60 days
- Current use of drugs that control diarrhea or affect peristalsis (e.g., loperamide. Opiates
 can be used in hospitalized patients and with outpatients if they are prescribed to a
 patient), or any anticipated use during the study
- Active drug, chemical, or alcohol dependency as determined by Investigator through history or urine toxicology screen
- Enrollment in any other investigational drug or device study known to interfere with Pepto bismol (bismuth subsalicylate) within the GI tract, within 30 days prior to Randomization (Day 1) or within 5 half-lives of the last dose of the previous investigational compound, whichever is longer. Vaccines are not exclusionary as they do not interfere with the mechanism of the study drug.
- Severe acute illness unrelated to COVID-19
- · Pregnant, breast-feeding, or considering becoming pregnant during the study
- · Planned hospitalization or surgery during the study
- Any medical, psychiatric, social, or other circumstances that may interfere with study compliance, completion, or accurate assessment of study outcomes

Standard therapy that is used for treatment of COVID-19 infection does not constitute an exclusion from this study.

3.3 Removal of Patients from the Study

During the study, patients will be withdrawn if any of the following applies:

- · Patient's request;
- Complicated COVID-19 infection that requires intubation;
- The Investigator determines that continued participation may cause harm. The Investigator always has the right to withdraw patients in the event of adverse events (AEs), intercurrent illnesses, protocol violations, laboratory abnormalities, treatment failure, or for administrative or other reasons:
- The patient becomes pregnant the treatment code will be revealed and the patient will be referred to an obstetrician and followed throughout the remainder of the study period

When possible, any patient who is withdrawn from the study during the treatment period will undergo all end-of-treatment (Day 21) procedures at the time of withdrawal, regardless of the length of treatment s/he received. Patients withdrawn from the study for medical reasons will remain under medical supervision until the Investigator deems the condition to be resolved or stabilized.

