Two specific papers have supported the use of Bismuth as a treatment option for COV+. [name] (Hong Kong) found that Bismuth was effective in inhibiting the SARS Corona virus helicase. Of note, this potential efficacy was noted by the Jinyintan Hospital during the current COV-19 pandemic. After several of their staff were infected, they used bismuth compounds prophylactically and noted no further infections.

These data point to the efficacy of preventing viral enteritis and low risk-profile for patients treated with BSS. Clearly, BSS may be part of a strategy for COV+ treatment given its low therapeutic risk profile and documented gut-virus clinical efficacy.

2. Study Objectives

The objectives of this pilot study are: To evaluate the tolerance and efficacy of BSS and SOC in mild/moderate severity COV+ population as defined by QRT-PCR of saliva or nasal swab samples compared to SOC and placebo and compare this efficacy to patients treated with SOC (placebo) alone. This will first be tested in 10 open-label patients, then in 2 groups of 25 patients as follows: Group one with mild/moderate disease and Group 2, patients with mild/moderate disease and persistently positive

for the SARS-Cov-2 virus by QRT-PCR testing for 14 days or more. This study is to assess the potential for BSS to influence the gut as a reservoir of infection by the SARS-Cov-2 virus and to determine the primary effect objective of change in stool frequency of patients treated with BSS compared to placebo treated patients.

Primary efficacy objective:

To determine whether treatment with BSS of Mild/Moderate COV+ decreases mean daily stool frequency compared to placebo-controlled patients

Secondary efficacy objectives:

Duration of hospitalization in BSS compared to PBO treated groups.

Weight gain (and BMI) relative to baseline at Week 1, and through Week 2.

Stool microbiota at baseline and Week 1, and through Week 2 (to be analysed at a later date).

To determine whether treatment with BSS of Mild/Moderate COV+ decreases the time to viral clearance (negative test by daily saliva testing) and persistently COV+ testing patients (over 14 days of COV+ testing) with Mild/Moderate disease, time until negative test by daily Saliva test.

3. Investigational Plan

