3.1 Study Design

This will be a 3 week, randomized, single-center, double-blind, proof-of-concept (POC) pilot study to evaluate the efficacy of patients with mild-moderate COVID-19+ infection. There will be an initial 10-pateint open-label study to assess patient tolerance to the active treatment arm of the study. The first 10 open-label patients will be treated with BSS 2 tablets PO (to chew) up to 4 times daily for 3 days (72 hours). The second 2 groups of patients will be mild (at home) or moderate (hospitalized, not on a ventilator) COV+ testing or with persistently + COVID testing for 14 days or more.

Patients will be allowed to receive a SOC treatment regimen at baseline (Appendix 2)

Standard of care (which includes any non-excluded SOC medications).

This pilot study will be conducted in the US in 1 center. A total of 60 patients are expected to be enrolled into the 3 arms of the study. Study one will consist of 10 open label COV+ patients with mild/moderate disease, the second and third studies will be double-blind placebo controlled studies of 25 patients each, the first with Mild/Moderate disease upon diagnosis by QRT-PCR+ testing and the third will consist of patients who are COV+, mild to moderate in severity with documented COV+ status by QRT-PCR testing for 14 days or more.

Screening will occur at the time patients are diagnosed via QRT-PCR testing. This may occur at one of several locations and/or time points of diagnosis:

- emergency room [ER]
- physician's office on the U of L campus.
- · University of Louisville hospitals (ULH Main and Jewish facilities).
- · Selected parking lot on UL campus.

 Campus Health (patients/students may be recruited via Practitioners or by approved recruitment flyers

Patients with initial COV+ confirmed by QRT-PCR testing will be approached to provide informed consent for the study. A third group of patients will be recruited with persistently + QRT-PCR testing for 14 days or more (see table 2).

Randomization will occur during SOC treatment.

Visits will occur at Baseline (Day 1) when patients will receive their first dose of study drug (BSS or PBO), and daily during the study until the patient tests COV- by saliva test or 21 days, whichever comes first.

The study design is depicted in Appendix 2.

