3.4.1.3 Daily Visits (1+/-21 Days)

The visits may occur daily up to Day 21(whichever comes first), or until the patient tests COVID- by saliva test. The following procedures will be performed at this visit:

- a. Medication history updated to include any changes or new medications since baseline;
- b. Recording of daily stool frequency and symptom questionnaire;
- c. Patient daily testing by saliva sample for COVID-19
- d. Assessment of AEs;
- e. Stool specimen collection at Day 7, Day 14 and Day 21. Collection kits to be given to patient 1 day prior if in an outpatient setting.

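### Patients who need intubation leave the study with no planned outcome follow-up, so viral clearance and hospital stay can lose data because of the outcome itself

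*Combined protocol and SAP*

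**What the plan says.** - **Withdrawal (Section 3.3).** "During the study, patients will be withdrawn if any of the following applies"; the list includes "Complicated COVID-19 infection that requires intubation". The section concerns removal from the study and does not separate that from stopping study drug.
- **After withdrawal (Section 3.3).** Where feasible, the patient "will undergo all end-of-treatment (Day 21) procedures at the time of withdrawal, regardless of the length of treatment s/he received". Those withdrawn for medical reasons "will remain under medical supervision until the Investigator deems the condition to be resolved or stabilized". No later collection of saliva results, discharge date or vital status is stated. The pregnancy item in the same list does require follow-up for the rest of the study period.
- **Endpoints (Sections 2 and 3.4.2).** The secondary objectives include "Duration of hospitalization in BSS compared to PBO treated groups" and time to viral clearance. Section 3.4.2 restricts time to a negative test to patients who reach clinical cure, meaning a negative saliva test.
- **Analysis (Section 3.6.1).** Saliva-negative rates at Weeks 1, 2 and 3 are compared, and are called primary there, although Section 2 makes stool frequency primary. Intent-to-treat appears only under safety. There is no efficacy set, no rule for missing data, censoring or competing events, and no dedicated analysis of hospitalization.
- **End of visits (Sections 3.1 and 3.4.1.3).** Visits are "daily during the study until the patient tests COV- by saliva test or 21 days, whichever comes first"; the procedures section repeats this with "or until the patient tests COVID- by saliva test".
- **Data collection (Appendix 1).** As far as the table is legible, no row records admission or discharge.

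**The concern.** Intubation is an outcome of the disease under study. If it removes a patient from follow-up, the patients who remain are selected by how well they did. An arm that loses its intubated non-clearers shows a higher clearance rate than it earned, and a long hospital stay may be missing or only partly counted. With 5 placebo patients planned per blinded study, one such patient is a fifth of the arm.

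A second gap has a different mechanism. A moderate patient may still be in hospital at the first negative saliva test. Visits stop, and no scheduled item then captures discharge. If stay were taken from visit records, an arm that clears virus faster would show a shorter stay simply because it was watched for less time. Duration of hospitalization also has no start, no end and no value for patients managed at home, although Section 3.1 enrols both settings.

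**Working it through.** **Inputs.** From the documents: two blinded studies of 25, each with 20 BSS and 5 placebo (Section 3.5.2), and a 21-day limit (Section 3.1). The documents give no intubation rate, clearance rate or length of stay, so there is no stated figure to reproduce. All such values below are assumptions.

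**1. Clearance rate, one intubated non-clearer excluded.** If c of n patients clear, the rate moves from c/n to c/(n − 1). With p = c/n, the shift is p/(n − 1).

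| Assumed cleared | Placebo, n = 5 | BSS, n = 20 |
|---|---|---|
| 40% | 2/5 = 40% → 2/4 = 50% | 8/20 = 40% → 8/19 = 42% |
| 60% | 3/5 = 60% → 3/4 = 75% | 12/20 = 60% → 12/19 = 63% |
| 80% | 4/5 = 80% → 4/4 = 100% | 16/20 = 80% → 16/19 = 84% |

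Pooling the two studies (10 placebo, 40 BSS) at 60% gives 6/10 → 6/9 = 67% and 24/40 → 24/39 = 62%.

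The 20:5 split conflicts with the coin toss in Section 3.5.1: a fair coin gives 5 or fewer placebo patients in 25 with probability 0.2%. With 12 or 13 placebo patients, the shift at 60% is 0.6/11 = 5.5 or 0.6/12 = 5.0 points.

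**2. Chance that the question arises.** With intubation risk q, the chance of at least one case is 1 − (1 − q)^n.

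| Assumed q | Any of 50 randomised | Any of 10 placebo |
|---|---|---|
| 2% | 64% | 18% |
| 5% | 92% | 40% |
| 10% | 99.5% | 65% |

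**3. Mean stay among inpatients.** Assume 7 days if not intubated; if intubated, a true stay of 20 days with withdrawal on day 4. The true mean is 7(1 − q) + 20q. Counting only to withdrawal gives 7(1 − q) + 4q, which is 16q lower. Dropping these patients gives 7.0.

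| Assumed q among inpatients | True mean | Counted to withdrawal | Dropped |
|---|---|---|---|
| 5% | 7.65 | 6.85 | 7.0 |
| 10% | 8.3 | 6.7 | 7.0 |
| 20% | 9.6 | 6.4 | 7.0 |

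**4. Stay recorded only to the last visit.** This was simulated with a true mean stay of 7.0 days (gamma, shape 4), independent exponential clearance times and visits ending at clearance or Day 21. Mean clearance of 7, 10 and 14 days gave recorded mean stays of 4.1, 4.8 and 5.3 days. The true stays were identical, so the differences come from follow-up alone.

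**The case against.** - **The documents do not say that a stay ends at withdrawal.** A reader might infer that intubated patients' stays are cut on the day they worsen. No section sets that rule. Section 3.3 keeps them under medical supervision, the study has one centre, and discharge dates could come from hospital records. This stands: step 3 shows what could happen, not what the plan prescribes.
- **The weekly saliva rates have no stated denominator.** Withdrawn patients could be counted as not negative, which would remove the shift in step 1. This stands for Section 3.6.1. It does not rescue the time measure in Section 3.4.2, which is restricted to patients who clear.
- **The first-negative rule does not discard the worst courses.** A reader might infer that it does. It ends visits for patients who clear, and for time to clearance that is the event itself. Its only risk here is unrecorded later inpatient days.
- **Bias between arms is not inevitable.** Excluding the same proportion from arms with equal clearance inflates both alike: losing 1 of 5 and 4 of 20 gives 3/4 and 12/16, both 75%. The direction cannot be known in advance.
- **Events may be rare.** Entry is limited to non-severe, non-ventilated patients, and hospitalization is a secondary objective of a pilot. Section 3.4.3 also asks about ventilation at each contact. That lowers the importance, but a safety question is not a plan for outcome data after withdrawal.

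**Conclusion.** The concern holds in this form. The plan removes patients from the study because they need intubation, states no outcome collection beyond one visit, and restricts time to a negative test to those who clear. It leaves open how withdrawn patients enter the weekly saliva rates and the hospital endpoint. This can bias two secondary endpoints, and also the saliva rates that Section 3.6.1 calls primary. The unrecorded inpatient days after a first negative test are a separate, smaller gap.

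Under an assumed 40% to 80% clearance, excluding one patient moves a placebo arm of 5 by 10 to 20 points and a BSS arm of 20 by about 2 to 4. These figures rest on the 20:5 split, which must be reconciled with the coin toss; a larger placebo arm shrinks the shift. The documents do not support a claim that stays are shortened by rule, or that either arm is favoured. The change is cheap and should be made.

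**What to change.** 1. In Section 3.3, separate stopping study drug from leaving the study. No change to when treatment stops is proposed.
2. For every randomised patient, whatever the saliva result and whether or not drug was stopped, abstract admission, discharge, ventilation and vital status from charts to Day 21, subject to consent. Add this to Appendix 1.
3. In Sections 3.4.2 and 3.6.1, analyse clearance in all randomised patients. Count intubation or death before a negative test as not cleared by Day 21 unless a negative result is on record. State how the Week 1 to 3 rates count a patient whose visits ended at an earlier negative test.
4. Define the hospital endpoint to a fixed Day 21 for everyone. One option is days alive and out of hospital, with days after death scored zero and patients never admitted (and alive to Day 21) scored 21.

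The cost is protocol and SAP wording, a small amount of chart abstraction at one centre, and a consent and IRB amendment to allow follow-up after study drug is stopped.

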3.4. Study Procedures

3.4.1 Schedule of Events

The schedule of events is displayed in tabular form in Appendix 2.

3.4.1.1 Screening Visit (Days -1 to 0)

Screening will occur at the time the diagnosis of COV+ is confirmed for the first study. For the second study, screening will occur at 2 weeks or more of documented COV+ status. During the screening visit

enrolled patients will be provided with a stool collection kit. Two patient groups will be studied: The following will be obtained to determine patient eligibility:

- a. Written or remote informed consent; (telephone and DocuSign)
- b. Demographic data;
- c. Medication history for the previous 30 days;
- d. Medical history including daily stool frequency;
- e. Social history (alcohol, tobacco, drugs);
- f. Height and Weight (which can be self-reported);
- g. Vital signs (temperature, pulse, blood oxygen saturation, blood pressure within 1 week of screening visit);
- h. Verbal affirmation that to the best of their knowledge they are not pregnant;
- i. Collection of serious, procedure-related non-treatment emergent AEs;
- Reminder for patients to avoid the use of protocol excluded medications for the duration of the study

All screening laboratory test results must be reviewed, signed, and dated by an Investigator when they are received (see list in Appendix 2).

3.4.1.2 Baseline Visit/Dosing (Day 1)

The baseline visit should occur within 2 days after the screening assessment. The following procedures will be performed at this visit:

- Medical and medication history update to include any changes or new medications since screening if applicable, and to ensure there is no change in medical condition that, in the Investigator's opinion, would interfere with study participation;
- b. Weight (which can be self reported);
- c. Recording of vital signs (temperature, pulse, blood oxygen saturation);
- d. Patient daily testing by saliva sample for COVID-19; Note: These data will not be reconciled with clinical data collected during the study. Saliva collection protocol:
 - a. The patient should not consume food or drink within 30 mins of sample collection
 - ID number placed on 15 ml collection tube and source docs so all samples/data can be reconciled.
 - Provide patient with sterile 15 ml falcon tube, ethanol wipe, and paper-covered straw.
 - d. The patient uses the straw to funnel spit into the collection tube. At least 1 ml of saliva should be collected. NOTE: saliva can be foamy, the foam does not count towards the 1 ml. Saliva collection may be undertaken inside the car with the window up.
 - e. Patient screws lid onto the tube, wipes down outside with ethanol wipe, and places into biohazard bag held by site personnel. The patient keeps straw and wipe and disposes of in the trash.
- Stool sample for bacterial speciation, metabolomics (at a later date). Collection kits will be provided at initial screening.
- f. Collection of serious, study procedure-related, nontreatment-emergent AEs;
- Review dosing instructions with the patient and stress the importance of compliance;
- h. Schedule all daily study visits.
- i. Recording of daily stool frequency and symptom questionnaire.

3.4.1.3 Daily Visits (1+/-21 Days)

The visits may occur daily up to Day 21(whichever comes first), or until the patient tests COVID- by saliva test. The following procedures will be performed at this visit:

- a. Medication history updated to include any changes or new medications since baseline;
- b. Recording of daily stool frequency and symptom questionnaire;
- c. Patient daily testing by saliva sample for COVID-19
- d. Assessment of AEs;
- e. Stool specimen collection at Day 7, Day 14 and Day 21. Collection kits to be given to patient 1 day prior if in an outpatient setting.

3.4.2 Efficacy Assessments

- Mean daily stool frequency and aggregate weekly stool frequency of treated versus placebo treated patients
- Time to negative test of subjects experiencing clinical cure (negative test of saliva-confirmed COV+infection).
- Incidence of Adverse Events (AEs)

3.4.3 Safety Assessments

Safety assessments will include the collection of AEs reported by the patient or observed by the investigator or study site personnel and will be reviewed by the Principal Investigator. Patients should be asked whether, since the time of the last observation or visit, they had any of the following:

- · experienced any changes in well-being,
- · used any new prohibited medications,
- · changed medication regimens (both prescription and over-the-counter), or
- · been hospitalized on a ventilator.

Questions should be of a general nature and should not suggest symptoms.

When an AE is suspected, all relevant evaluations will be carried out and appropriate treatment provided. Additional follow-up will be performed as necessary, recorded in the patient's source documents, with the results provided to the Sponsor. Patients who experience any clinically significant AE will remain under medical supervision until the Investigator deems the AE to be resolved, stabilized, or no longer serious enough to warrant follow-up. Laboratory values that are abnormal and not assessed as AEs may be followed at the discretion of the Investigator Monitor until resolved or stabilized.

Symptoms will not be considered AEs unless the symptom meets the International Conference on Harmonization (ICH) definition of a serious AE or the patient withdraws from the study due to the symptom. Symptoms meeting either of these 2 conditions will be recorded on the AE log page so that the event can be assessed for immediate reportability.

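### The only hospitalization question in section 3.4.3 is limited to ventilated patients, and no listed procedure records hospital status or admission and discharge dates

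*Combined protocol and SAP*

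**What the plan says.** Section 3.4.3 sets the interview: "Patients should be asked whether, since the time of the last observation or visit, they had any of the following". Four topics follow. One is open ("experienced any changes in well-being"), two concern medication, and the fourth is whether the patient has "been hospitalized on a ventilator". Section 3.4.3 also takes AEs from observation by the investigator and site staff.

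The same section restricts what is logged: "Symptoms will not be considered AEs unless the symptom meets the International Conference on Harmonization (ICH) definition of a serious AE", or unless the patient withdraws because of the symptom.

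Section 3.1 describes the blinded groups as "mild (at home) or moderate (hospitalized, not on a ventilator) COV+ testing" or persistently positive. Both at-home patients and inpatients are therefore enrolled.

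Section 2 names as a secondary objective "Duration of hospitalization in BSS compared to PBO treated groups".

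On contact frequency, section 3.4.1.3 states: "The visits may occur daily up to Day 21(whichever comes first), or until the patient tests COVID- by saliva test". Appendix 1 marks the Day 2-21 column as optional.

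**The concern.** An at-home patient who is admitted to a ward without ventilation has moved from the protocol's mild category to its moderate one. Asked the hospital question as written, that patient can truthfully answer no. Two uses of the data depend on the answer.

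- **Safety.** For a symptom, seriousness is one of only two ways onto the AE log. If an admission is not known, the seriousness assessment that it might trigger may not take place.
- **Efficacy.** A comparison of time in hospital needs dates. If no procedure collects them, the objective rests on whatever happens to be in other records, and these may be less complete for patients who started at home.

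**Working it through.** The plan gives no figure to reproduce, so the check is mainly a comparison of sections.

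**1. Follow one event, a home-to-ward admission without ventilation, through the four topics in section 3.4.3.**

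| Topic | Would it bring the admission out? | Would it yield dates? |
|---|---|---|
| Well-being | Possibly; open question, admission not named | No |
| New prohibited medication | Only if one was given | No |
| Changed regimen | Possibly, if treatment changed | No |
| Hospital care with ventilation | No; the truthful answer is no | No |

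**2. Look for another place where it is recorded.**

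- Section 3.4.1.1 (screening) lists history, medication, height and weight, vital signs and similar items. Section 3.2.1 makes the care setting part of eligibility, but the screening list has no status or date field.
- Section 3.4.1.2 (baseline) has no such item.
- Section 3.4.1.3 (daily visits) lists medication update, stool frequency and symptom questionnaire, saliva, AEs and stool specimens. It refers to an outpatient setting only to time the kit handout.
- Appendix 1 has no row for hospital status, admission or discharge.
- Section 3.4.2 does not list hospitalization among the efficacy assessments.

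**3. Consequence for the AE log.** Section 3.4.3 gives two routes for a symptom to become an AE: it is serious under the ICH definition, or the patient withdraws because of it. The protocol cites that definition without setting it out; I assume that it counts inpatient admission. Section 3.3 does not make a non-ventilated admission, by itself, a reason for withdrawal. Whether the symptom is logged can therefore depend on site staff learning of the admission. The ventilator question, by contrast, largely overlaps with a withdrawal ground already in section 3.3 (need for intubation).

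**4. Consequence for the secondary objective.** Duration = discharge date minus admission date, summed over stays. For a patient at home on Day 1, both dates are needed. For a patient already in hospital, the discharge date is needed and may fall after follow-up has ended, because visits stop at a negative saliva test or Day 21. None of these dates is listed, so the gap affects both kinds of patient. Section 3.6.1 has only a general clause for continuous endpoints and does not say how a stay is counted.

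**5. Size.**

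- Section 3.5.2 gives 20 BSS and 5 placebo in each of two groups: 2 × 20 = 40 BSS and 2 × 5 = 10 placebo. One unrecorded admission is 1/10 = 10% of the placebo arm or 1/40 = 2.5% of the BSS arm.
- Section 3.5.1 describes a coin toss instead. If the coin is fair, 50/2 = 25 are expected per arm, and one admission is 1/25 = 4%.
- The at-home share and the admission rate are not in the documents. Purely as an illustration, assume that half of the 50 blinded patients are at home and that 5% to 15% are admitted without ventilation: 25 × 0.05 = 1.25 and 25 × 0.15 = 3.75 admissions. For all 60 patients the same assumptions give 30 × 0.05 = 1.5 to 30 × 0.15 = 4.5, but that total includes the 10 open-label patients, who are treated for only 3 days. These are admissions not directly asked about, not admissions missed.

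**The case against.** The strongest reply is that not being asked directly is different from being missed. An admission for worsening illness would often produce a yes to the well-being question or the regimen question. Staff may observe it, and AE assessment also takes place at unscheduled visits. Staff need to know the care setting to hand out kits and to apply the opiate rule in section 3.5.5. Section 3.4.3 lists topics rather than a verbatim script, and the case report forms are not part of the documents. All of this stands, and it limits the claim: the admission is detectable, but its detection is left to indirect routes, and none of those listed yields the dates.

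The present wording also has a plausible reason. Moderate patients are already in hospital, so a bare question about being hospitalized would tell the site nothing about them, whereas ventilation matches a withdrawal ground. That argues for two questions, one on new admission and one on ventilation, and not for leaving the first one out. The instruction that questions stay general and not suggest symptoms is no obstacle: an admission is an event, and the list already asks about a narrower version of it.

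A reader might infer that section 3.3 withdraws patients only for intubation, so that an admitted patient always stays in the trial. The section does not say that. It also allows withdrawal at the patient's request, for expected harm, and at the investigator's discretion for AEs, intercurrent illness, laboratory abnormalities, treatment failure and other reasons. The supportable statement is that a non-ventilated admission does not by itself require withdrawal.

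**Conclusion.** The point holds as one of data capture and should be corrected. The hospital question is narrower than the enrolled population and the secondary objective require, and no listed procedure supplies the missing dates. That finding rests on the text alone. The safety consequence also rests on the assumption that the cited ICH definition counts inpatient admission.

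Three stronger readings are not supported:

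- That admission is the main route by which a symptom becomes an AE. Section 3.4.3 gives two routes and does not rank them.
- That between one and four serious events would be missed. The inputs behind such a count are assumed, and it would require every indirect route to fail.
- That an at-home patient admitted later would be scored as having spent no time in hospital. No scoring rule is given, so this can be neither confirmed nor excluded.

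The effect on the treatment comparison cannot be estimated from the documents. With as few as 10 placebo patients, however, a single unrecorded stay would be visible in the result.

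**What to change.** 1. In section 3.4.3, ask about any new hospital admission since the last contact, with dates and reason. Make ventilator use a separate item.
2. Add current hospital status, with admission and discharge dates, to the list in section 3.4.1.3 and to Appendix 1. Include the discharge date for patients in hospital at baseline, and a way to obtain it when the stay outlasts the last visit.
3. State that any new admission after the first dose is entered on the AE log and assessed for seriousness.

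The first and third items address safety capture. The second is needed for the secondary objective and would still be needed if only the question were reworded. The cost is one reworded question, one added item and a short status field at contacts already planned, some follow-up for late discharges, and a few more reports to process. Treatment and care are unchanged.
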